Mobile phone reminder system: Participants in Arms 2 and 3 receive reminders for upcoming vaccination appointments 1 week and 1 day before the vaccination due date. No reminders are associated with the EDD or the vaccination due at birth. Reminders are issued in the form of text messages to the mobile phone numbers of study participants or their designees. Prior to study implementation, messages were tested for comprehension using a structured template, and revised based on feedback received. The timing of messages is based on findings from a cross-sectional survey of 134 Tanzanian mothers of children ages 12-23 months. In that survey, 54% of women who indicated any mobile phone use wanted to receive reminders one week before the due date, 40% one day before the due date, and 6% on the due date. Data on comprehension are collected in the end-line survey to inform future implementations.

Incentive disbursement system: For each timely vaccination for which a reminder with an incentive offer was sent to a mobile phone, a payment in the form of a mobile phone airtime recharge voucher code (worth either TSH 1000 or TSH 2000) is sent to a mobile phone number specified by the participant. The two-tiered incentive amount, which was chosen ad hoc by the study team as appropriate to 'nudge' participants toward timely vaccinations without significantly changing their economic incentives, [37] is conditional upon the timing of vaccination (see below).

Technical implementation: The scheduling and sending of SMS messages and incentives is implemented via a custom-built task scheduling, execution, and event tracking application called mParis ("mobile phone assisted reminder and incentive system"). mParis, which was developed for another NIH-funded study (R01MH106388), is built using Flowable, a flexible, open source, Java-based, workflow engine (<https://www.flowable.org>). [38] The system is based at the Kilimanjaro Clinical Research Institute, in Moshi, Tanzania.

Study activities

Key events and related study activities are summarized in **Figure 1** and **Table 3**.

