Women providing informed consent are enrolled in the study. At the time of enrollment, a baseline survey is conducted with all participants to assess socio-demographic characteristics, mobile phone ownership and use, reproductive history, EDD for the current pregnancy, and vaccination knowledge, history of vaccinations in a prior child, if applicable, and previously experienced or anticipated barriers to vaccinations. Mobile phone numbers are obtained for mothers and any authorized agents. Surveys are implemented electronically on tablet devices

and conducted by study staff at health facilities, participants' homes, or other mutually agreed-upon locations.

Toward the end of Phase 1, all women are contacted by phone to ascertain birth dates and outcomes, and information on past and scheduled vaccinations. The information is used to generate child-specific vaccination schedules. In Phases 2 and 3, reminder messages are sent to registered mobile phone numbers 1 week and 1 day prior to each scheduled vaccination, and, if no vaccination confirmation is received, 2 weeks after the vaccination due date. Uniquely numbered cards, given to participants at each completed or rescheduled vaccination, allow participants to report vaccination dates via the USSD system. When no vaccination report is received via the USSD system, SMS, or phone calls from participants, study staff contact the participant by phone to verify whether and when a vaccination was received, and ascertain the due date for the next vaccination, if applicable. Recorded vaccination dates are used to iteratively update vaccination schedules and to re-schedule reminders.

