For each participant, outcomes are observed at three time points (corresponding to timely vaccinations at 6, 10 and 14 weeks, respectively). The probability of timely vaccinations and its association with reminders and incentives will be analyzed using a random effects logistic regression model. The outcome variable is 1 if the vaccination was received on-time, and 0 if early, delayed, or not received at all. The primary covariates of interest are indicator variables for the receipt of reminders only (“*reminder*”) and the receipt of reminders with an incentive offer (“*reminder+incentive*”). For arm 1 the value of both covariates is 0 for all three time points. For outcomes in arm 2, the value for *reminder* (and for arm 3 the value for *reminder+incentive*) is 1 if the mHealth system confirmed delivery of the reminder, and 0 for all other observations. Additional covariates (e.g. mother’s education, rural vs. urban residence, recruitment from health facilities vs. the community) will control for differences in participant characteristics between study arms and their association with vaccination timeliness. Interactions of *reminder* and *reminder+incentive* with these covariates describe systematic variation in the effects of reminders and incentives on vaccination timeliness. Models will control for the number of phone-based contacts prior to or within the timeliness window for any given vaccination, and standard errors will be adjusted to account for clustering at the level of the health facility catchment area.

Statistical power

Across 400 participants we expect up to 1,200 data points on vaccination timeliness. Assuming (a) that these data points are distributed equally across the 3 study arms (standard of care; reminders only; reminders and incentive); (b) a 10% attrition rate; (c) equal cluster sizes of 10 women per health facility catchment area, with an intra-cluster correlation of 0.02; (d) 3 observations per child, with a within-child correlation of 0.2; (e) a baseline rate of vaccination timeliness of 65% in the control condition; and (f) a 10 (15) percentage point difference associated with reminders (reminders and incentives), the power ($\alpha=.05$, 2-tailed) to detect such difference is 72% (98%).

Dissemination

Results will be shared with stakeholders at the regional and national levels, presented at national and international conferences, and published in high impact academic journals.

Data sharing

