mHealth-Assisted Conditional Cash Transfers to Improve Timeliness of Vaccinations (MINT)

ClinicalTrials.gov ID NCT03252288

Statistical analysis

For each participant, outcomes are observed at three time points (corresponding to timely vaccinations at 6, 10 and 14 weeks, respectively). The probability of timely vaccinations and its association with reminders and incentives will be analyzed in a bivariable analysis and using a random effects logistic regression model. The outcome variable is 1 if the vaccination was received on-time, and 0 if early, delayed, or not received at all. The primary covariates of interest are indicator variables for the receipt of reminders only (“*reminder*”) and the receipt of reminders with an incentive offer (“*reminder+incentive*”). For arm 1 the value of both covariates is 0 for all three time points. For outcomes in arm 2, the value for *reminder* (and for arm 3 the value for *reminder+incentive*) is 1 if the mHealth system confirmed delivery of the reminder, and 0 for all other observations. Additional covariates (e.g. mother’s education, rural vs. urban residence, recruitment from health facilities vs. the community) will control for differences in participant characteristics between study arms and their association with vaccination timeliness. Interactions of *reminder* and *reminder+incentive* with these covariates describe systematic variation in the effects of reminders and incentives on vaccination timeliness. Models will control for the number of phone-based contacts prior to or within the timeliness window for any given vaccination, and standard errors will be adjusted to account for clustering at the level of the health facility catchment area.

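### The SAP does not pre-specify the unreminded birth dose as a baseline covariate; naming it would improve balance between birth cohorts and give a modest gain in precision

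*SAP*

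**What the plan says.** The SAP (Statistical analysis) plans a bivariable analysis and a random effects logistic model for on-time vaccination at 6, 10 and 14 weeks. Its additional covariates are introduced by an e.g.: mother's education, then "rural vs. urban residence, recruitment from health facilities vs. the community) will control for differences in participant characteristics between study arms". The model also controls for the number of phone contacts. The Protocol's Statistical analysis section gives the same list. Neither document names any earlier timeliness measure as a covariate.

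Three places in the Protocol bear on whether such a measure exists:

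- Mobile phone reminder system: "No reminders are associated with the EDD or the vaccination due at birth". Reminders start one week before a due date.
- Study activities: toward the end of Phase 1 every woman is phoned about the birth and for "information on past and scheduled vaccinations".
- Study activities: the end-line survey, 12 months after enrolment, records vaccination dates from the government-issued card.

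The baseline survey also asks about vaccinations of a prior child, but only some women have one.

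**The concern.** The named covariates are indirect markers of a family's tendency to vaccinate on time. Birth-dose receipt is a direct one. The earliest possible reminder for the 6-week visit falls at about day 42 − 7 = 35, so receipt by day 28 is settled before any study reminder, whichever arm the later events fall in. It can serve as a baseline covariate.

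This matters more here than in an individually randomised trial. Under the Protocol's assignment section, arm is set by calendar due date. A child's three visits span 14 − 6 = 8 weeks, so on the original schedule no child can contribute to both control and reminder+incentive if Phase 2 lasts longer than that. Much of that contrast is then between children born at different times, and cohort or chance differences in the tendency to vaccinate on time pass straight into it. An open list neither guarantees that the best available covariate is used nor prevents covariates from being chosen after the results are seen.

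**Working it through.** **Inputs from the Protocol (Statistical power).**
- "Across 400 participants we expect up to 1,200 data points on vaccination timeliness".
- Equal arms ("that these data points are distributed equally across the 3 study arms").
- "a 10% attrition rate", which leaves 360 events per arm and 1,080 in all.
- Three observations per child, within-child correlation 0.2.
- "equal cluster sizes of 10 women per health facility catchment area, with an intra-cluster correlation of 0.02".
- Control rate 65%; effects of 10 and 15 percentage points; two-sided 0.05; stated power 72% and 98%.

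**Assumptions, not in the documents.**
- Correlation r between birth-dose timeliness and each later visit: 0.2, borrowed from the within-child value, with 0.1 and 0.3 as the range.
- Births spread evenly over 8 to 39 weeks, with the two transition dates at the terciles of due dates.
- A linear generalised least squares (GLS) approximation to the logistic model.

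**1. The plan's own figure.** The within-child design effect is 1 + 2 × 0.2 = 1.4, so effective n per arm = 360/1.4 = 257. Power = Φ(difference/√[(p₁q₁ + p₂q₂)/n] − 1.96).
- Reminder: 0.10/√(0.415/257) = 2.49, giving 70.2%.
- Reminder+incentive: 0.15/√(0.3875/257) = 3.86, giving 97.2%.

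Both are within 2 points of the stated 72% and 98%. Multiplying in the full facility design effect (1 + 9 × 0.02 = 1.18; 1.4 × 1.18 = 1.652) gives about 63% and 94%, which does not match. That is a separate matter. The steps below scale the stated powers.

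**2. What the covariate can and cannot remove.** Given the birth dose, each event has variance 1 − r² and each pair within a child has covariance 0.2 − r².
- Wholly within-child contrast: the variance of a difference is 2(1 − 0.2) with or without the covariate. Gain: zero.
- Wholly between-child contrast: the variance of a child mean is 1.4/3 = 0.467 and falls by r². At r = 0.2 that is 0.04/0.467 = 8.6%. This is the ceiling at r = 0.2, and it would move 72% to about 76% and 98% to about 98.7%.

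**3. The calendar roll-over lies in between.** Variance reduction at r = 0.2, over and above what an exchangeable within-child correlation already handles:

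| Birth spread | Model as written: reminder / reminder+incentive | With visit terms |
|---|---|---|
| 8 weeks | 0.6% / 2.0% | 2.9% / 5.7% |
| 13 weeks | 1.2% / 3.3% | 2.9% / 6.1% |
| 26 weeks | 3.5% / 6.1% | 3.9% / 7.0% |
| 39 weeks | 4.9% / 6.8% | 5.0% / 7.3% |

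The SAP names no terms for visit (6, 10 or 14 weeks), so the left-hand column is the one that applies to the plan. The largest reduction in the table (variance ratio 0.927) equals 1,080 × (1/0.927 − 1) ≈ 85 extra events.

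**4. Effect on stated power.** New power = Φ((z_P + 1.96)/√ratio − 1.96), where z_P is the normal quantile of the stated power. For reminder at 39 weeks as written: (0.583 + 1.96)/√0.951 − 1.96 = 0.65, or about 74%. Across the table, 72% becomes about 72–74% and 98% becomes about 98.2–98.6%.

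**5. Sensitivity to r, both models together.** At r = 0.1 the reductions are about 0–1% (reminder) and 0.5–2% (reminder+incentive). At r = 0.3 they are about 1–12% and 5–17%.

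**6. Ceiling on r.** For a yes/no covariate with on-time rate b, against a 65% outcome, r cannot exceed √[(1 − b) × 0.65/(b × 0.35)]. That is 0.31 if b = 95% and 0.24 if b = 97%. The documents give no birth-dose rate.

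**The case against.** The case against is that this is an optional covariate with a small gain. Much of it stands.

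- A reader might infer that the model adjusts for no earlier behaviour at all. The documents do not support that: the list is open, and it could take in the birth dose or the prior-child history. The weakness is lack of pre-specification.
- A reader might infer that the gain is free and the data are already in hand. Neither document says that the birth-dose date is recorded; it follows by inference from the phone interview and the card review. The Protocol's Discussion warns that client-reported dates may be inaccurate.
- Some children will lack the date, partly because of loss to follow-up, and the Protocol ties loss to follow-up to non-delivery of reminders. Missingness may therefore relate to both exposure and outcome. This changes how the fix should be worded but does not defeat it.
- The value 0.2 describes the three later visits, not the birth dose. A value above it would need the birth dose to predict later visits better than they predict one another.
- Reminder+incentive already has 98% stated power, so little is gained there beyond a slightly narrower interval.

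One objection does not stand: that a child-level random effect already does this work. It models the correlation but does not remove between-child differences from a between-child contrast. The reductions in the table already allow for within-child correlation.

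**Conclusion.** The point holds as a minor improvement. The SAP leaves unnamed a covariate that precedes every reminder, measures the same behaviour and is very probably recorded for followed children. At an assumed correlation of 0.2 it lowers variance by about 1–5% for reminder and 2–7% for reminder+incentive in the model as written, or 3–5% and 6–7% if visit terms were added. That is worth at most about two points on 72% and well under one point on 98%. In this calendar-based design, balance between birth cohorts may be the stronger reason for it.

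The size rests on the assumed correlation, the assumed spread of births and a linear approximation. It shrinks toward nothing if nearly all birth doses are on time or if the contrasts are mostly within child. It does not show the planned analysis to be wrong.

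**What to change.** Add one line to the SAP naming as a pre-specified covariate of the primary model: birth-dose vaccination received within 28 days of birth (yes/no), taken from the vaccination card, with the phone report used only where no card date exists.

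Do not substitute timeliness at 6 or 10 weeks, which can follow exposure to a reminder.

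The cost is that line, confirmation that the date is captured, and a missing-data caveat. Report the number of children without the date by arm, and show the result with and without the covariate. No new data collection appears to be needed.

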Since the study includes participants ages 16 years and older, the Institutional Review Board (IRB) granted a waiver of parental consent for pregnant women ages 16 and 17 years old. Tanzanian national policy indicates that adolescents under age 18 who are sexually active are considered “mature minors”, have the right to access reproductive health services without parental or spousal consent, and can make associated medical decisions on their own behalf. [36] Given that sexually active adolescents have this “adult” right to medical decision-making, it was determined that pregnant adolescents ages 16 and 17 years are also able to consent to research participation for themselves without parental or spousal consent.

No blinding

The nature of the interventions, mobile phone-based reminders and incentives in the form of CFTs, precludes blinding of study participants.

Intervention components and implementation

For the delivery of the study interventions, we developed an mHealth system comprising the following components:

Scheduling system: Upon enrollment, a participant’s name, contact information, and EDD are stored in a database, and participants are added to a process queue. For each participant, the process awaits inputs (e.g., date of birth of the child, vaccination dates) and executes tasks according to a pre-specified schedule. Tasks include sending reminder SMS, tracking SMS delivery, and alerting study staff to call participants when follow-up action is required. When event-related inputs (e.g. dates of completed or rescheduled vaccinations) are received by the system, the database and the schedule of tasks are updated. For example, a delay in one vaccination shifts the remaining schedule by the length of the delay.

USSD notification system: Participants can notify the scheduling system of events (e.g., birth of child, vaccinations received) using an Unstructured Supplementary Service Data (USSD) dialog. USSD dialogs, which can be accessed free of charge by dialing a short code from any mobile phone, allow for a two-way exchange of data. In this case, the USSD dialog is implemented analogously to a short survey. Participants are guided through text-based menus which prompt them for information related to the event they are reporting. The information is passed to the scheduling system, which updates the schedule of upcoming tasks.

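### The adjusted model counts phone contacts up to the end of the 28-day outcome window; some of these result from the outcome, so the reminder coefficients can be biased by an amount the documents do not fix

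*SAP*

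**What the plan says.** The sentence "Models will control for the number of phone-based contacts prior to or within the timeliness window for any given vaccination" stands in the SAP and in the Protocol's Statistical analysis section. Neither document defines a phone-based contact. It could mean staff calls, participants' calls, USSD reports or SMS, and the count could be cumulative or per vaccination. The Protocol's Outcome measures section sets the window at 28 days from the due date. The outcome is 1 if the vaccination was on time and 0 if it was early, late or never given.

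Study activities describes these contacts:

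- **All women, once:** "Toward the end of Phase 1, all women are contacted by phone to ascertain birth dates and outcomes".
- **Automated SMS inside the window, Phases 2 and 3:** an extra reminder, "if no vaccination confirmation is received, 2 weeks after the vaccination due date".
- **Staff calls, day not given:** "When no vaccination report is received via the USSD system, SMS, or phone calls from participants, study staff contact the participant by phone".
- **Participants' reports:** "Uniquely numbered cards, given to participants at each completed or rescheduled vaccination, allow participants to report vaccination dates via the USSD system".

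The Scheduling system paragraph adds that the system's tasks include "alerting study staff to call participants when follow-up action is required". The Discussion accepts that staff follow-up calls could act as an intervention in their own right, which is the apparent reason for the covariate.

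**The concern.** A covariate in a model for timely vaccination should be settled before the outcome. Here part of the count is produced by it. The 2-week SMS and the no-report calls become more likely when the child has not been vaccinated. Participants' reports become more likely when the child has been.

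If the count also differs by phase, adjusting for it moves the arm coefficients. As a linear approximation, adjusted coefficient = unadjusted coefficient − γδ, where γ is the association of the count with timeliness within arm and δ is the arm difference in mean count. With δ > 0, no-report calls (γ < 0) push the estimate up and participants' reports (γ > 0) push it down.

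This is the only multivariable model in the plan. Two analysts could follow the sentence faithfully, count different contacts, and reach different reminder effects. The SAP's bivariable analysis is free of the problem, but only because it drops all covariate adjustment, in a design where arm is set by calendar phase.

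**Working it through.** **1. The plan's own figures, for scale.** Statistical power assumes 65% timely under control, 75% with reminders and 80% with reminders plus incentives. The odds ratios are (0.75/0.25)/(0.65/0.35) = 1.62 and (0.80/0.20)/(0.65/0.35) = 2.15. The stated power of 72% (98%) can be approximated. There are 400 × 0.9 = 360 events per arm. The design effect is [1 + 9 × 0.02] × [1 + 0.5 × 0.2] = 1.18 × 1.10 = 1.298, if a child contributes 1.5 events per arm (assumed). That leaves 277 effective events and power of 73.0% (97.9%). This power does not depend on the contact covariate.

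**2. A case that can be checked by hand.** Assumptions, none from the documents except the 65%: one vaccination, no true effect, 45% vaccinated on time by day 14 and a further 20% by day 28, half of vaccinations self-reported, 80% of unreported events called on day 14, calls in the reminder arm only, every reminder confirmed. The chance of escaping a call is 0.6 for a child vaccinated by day 14 (0.5 + 0.5 × 0.2) and 0.2 otherwise. Since arm 1 has no calls, the adjusted arm effect compares uncalled reminder-arm events with arm 1 (odds 0.65/0.35 = 1.857).

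- Uncalled and timely: 0.45 × 0.6 + 0.20 × 0.2 = 0.31.
- Uncalled and not timely, none early: 0.35 × 0.2 = 0.07. Odds 4.43, OR 4.43/1.857 = 2.38.
- With 10% early: 0.10 × 0.6 + 0.25 × 0.2 = 0.11. Odds 2.82, OR 1.52.
- With 20% early: 0.20 × 0.6 + 0.15 × 0.2 = 0.15. Odds 2.07, OR 1.11.

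The true OR is 1.00 throughout. Early vaccination weakens the bias because an early child who reports is not called yet scores 0. If 10% of reminders are unconfirmed, and so coded 0 as the SAP prescribes, the same calculation gives 1.90, 1.39 and 1.09.

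**3. Simulation of the full design, no true effect.** Three events per child 28 days apart, births uniform over 150 days, T2 and T3 at thirds of the events, child random intercept SD 1.1, 90% confirmed delivery, one call to all women in the last 3 weeks of Phase 1, random-intercept logistic model; otherwise as in step 2. Rescheduling after a delay is not modelled. Entries are ORs for reminder / reminder+incentive. Where two pairs appear they come from separate simulations.

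| Contacts counted | OR |
|---|---|
| Cumulative staff calls, day 14, Phases 2-3, none early | 1.39 / 1.88 to 1.45 / 1.94 |
| Same, 10% early | 1.24 / 1.46 and 1.21 / 1.46 |
| Same, 20% early | 1.07 / 1.13 and 1.06 / 1.14 |
| No-report calls in all phases, cumulative, none early | 1.23 / 1.40 and 1.17 / 1.39 |
| No-report calls in all phases, per vaccination, none early | 1.01 / 1.00 |
| Staff calls on day 35 | 1.00 / 1.00 |
| Participants' reports instead of no-report calls, cumulative | 0.53 / 0.47 |
| Same, per vaccination | 0.78 / 0.77 |

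A further simulation with other assumptions and the planned effects built in gave larger upward bias for a single day-14 call: +0.72 / +1.44 on the log odds scale. The size therefore depends heavily on the inputs.

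**4. Counting only staff calls before the due date.** In the day-14, Phases 2-3 scenarios the ORs were 1.01-1.04 / 1.04-1.09 (1.03-1.06 / 1.07-1.10 in a repeat). With calls in all phases they were 1.05 / 1.06, and with day-35 calls 1.00 / 1.01. A model with no count gave 1.00 / 1.00-1.03.

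**5. Precision at 360 children.** The SE relative to a model with no count is 1.10 / 1.32 for the pre-due count and 1.09 / 1.27 for the cumulative count as written. If the stated 72% / 98% is taken as the no-count model's power, then Φ[(1.96 + z_power)/ratio − 1.96] gives about 64% / 86% and 65% / 89%.

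**The case against.** - **Staff calls may be a co-intervention, so they should be adjusted for.** This stands for calls made before the due date, and the fix can keep them. It does not justify conditioning on contacts prompted by non-vaccination or made after vaccination.
- **The inputs are unknown.** This stands. If only staff calls count and they fall after day 28, nothing is biased. The phase difference is also an inference. Study activities sets out one call to all women in Phase 1 and follow-up in Phases 2-3, but it does not rule out no-report calls in Phase 1, and on enrollment "participants are added to a process queue". "Key events and related study activities are summarized in" a figure and a table that are absent from the text available here and may settle it.
- **A reader might infer that the bias is as large as the planned effects.** The 1.4 / 1.9 figure needs day-14 calls and no early vaccinations. The outcome definition expressly provides for early ones, and at 20% early the bias is small.
- **A reader might infer that upward and downward bias are equally likely.** The Protocol mostly describes staff as contacting and participants as reporting. The downward results come mainly from counting participants' reports. One single-run exception (0.81 / 0.63) needs no-report calls in all phases, counted per vaccination, plus the Phase 1 call.
- **A reader might infer that the pre-due count beats having no count.** The figures do not show this. With no call effect, the no-count model is unbiased and more precise. If the Phase 1 call has an assumed lasting OR of 1.3, the pre-due count moves 1.19 / 1.19 only to 1.16 / 1.13.
- **The bivariable analysis is unaffected, and neither document names the adjusted model as primary.** True, and it limits the damage, but the adjusted estimates remain exposed.

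**Conclusion.** The concern holds. As written, the model conditions on contacts that are partly a consequence of the outcome, and the term that decides which contacts count is undefined. Neither point depends on the simulations.

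The direction is upward where in-window no-report calls are counted and accumulate more in arms 2 and 3; it can be downward where participants' reports are counted. With no true effect, the illustration runs from about 1.4 / 1.9 (none early) through 1.2 / 1.5 (10% early) and 1.1 / 1.1 (20% early) to about 1.0 / 1.0 (staff calls after day 28). It rests on assumed call days, reporting rates and early shares, and is not a forecast of the error in this trial. The documents support neither one headline size nor a ranking of the pre-due count above no count. The plan should be corrected before analysis; confidence is medium because the size is unknown, while the mechanism is clear.

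**What to change.** 1. Define a phone-based contact as a staff-initiated call, and state when staff calls are made and in which phases.
2. Replace the present time limit with calls made before the due date of the vaccination being analysed. No contact after the due date, automated SMS or participant report is then counted.
3. Report the adjusted model with and without this count side by side, and the count as now written as a sensitivity analysis.
4. Tabulate contacts by arm, timing and outcome.

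**Cost:** SAP wording, two further model fits and one table. The dated contact records are already needed for the present covariate.

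**Downsides:** The pre-due count costs precision against no count (SE about 1.1 / 1.3 times), much as the present plan does. It leaves a small residual bias, because earlier calls can reflect earlier missed vaccinations, and it removes little of any true effect of the end-of-Phase-1 call. Any true effect of in-window calls stays in the arm estimates (1.21 / 1.22 if day-14 calls in Phases 2-3 have an assumed OR of 1.3). Those estimates should then be described as the effect of reminders plus follow-up calls.
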